### **8.3 Safety Set**

The **Safety Set** will include all subjects who received at least 1 dose of study drug. The Safety Set will be used for all safety analyses in which subjects will be analyzed according to the treatment they received, unless otherwise specified.

## 9 STATISTICAL ANALYSIS

### 9.1 General Considerations

The Schedule of Assessments is provided in Section 3 of CSP. The precision standards for reporting safety variables are provided in an internal Biometrics document that specifies the programming rules including the precision for derived variables.

**Continuous variables** will be summarized using the following descriptive summary statistics: the number of subjects (n), mean, SD, median, minimum value (min), and maximum value (max).

**Categorical variables** will be summarized using counts and percentages.

**Baseline value**, unless specified otherwise, will be defined as the most recent non-missing measurement (scheduled or unscheduled) collected before the first dose of study drug. For ECGs, the baseline value will be defined as the average of the non-missing pretreatment measurements (triplicate) collected before the first dose of study drug. For subjects who have ever been on augmentation therapy at any time, only functional and antigenic AAT levels collected >42 days after the last dose of augmentation therapy can be used to define baseline values. For functional and antigenic AAT levels, only the screening results obtained from the assay for Day 1 to Day 28 can be used to define baseline values if the Day 1 pre-dose results are missing.

**Change (absolute change) from baseline** will be calculated as Post-baseline value – Baseline value.

**Relative change from baseline** will be calculated and expressed in percentage as  $100\% \times (\text{post-baseline value} - \text{Baseline value}) / \text{Baseline value}$ .

**Treatment-emergent (TE) Period** will include the time period starting from the date of the first dose of study drug to either (1) Safety Follow-up Visit 28 days after the last dose of study drug, (2) ETT Visit if it replaces the Safety Follow-up Visit 28 days after the last dose of study drug, or (3) 28 days after the last dose date for subjects who do not have a Safety Follow-up Visit 28 days after the last dose or an equivalent ETT.

For subjects consented to the study under CSP Versions 1.0, 1.1, and 1.2, the TE period will include the time period starting from the date of the first dose of study drug to either (1) Safety Follow-up Visit 14 days after the last dose of study drug, (2) ETT Visit if it replaces the Safety Follow-up Visit 14 days after the last dose of study drug, or (3) 14 days after the last dose date

for subjects who do not have a Safety Follow-up Visit 14 days after the last dose of study drug or an equivalent ETT.

**Unscheduled visits:** Data obtained from unscheduled visits will be included in the analysis as follows:

- In scheduled visit windows per specified visit windowing rules
- In the derivation of baseline and last on-treatment measurements
- In the derivation of maximum and minimum values during TE period, and maximum and minimum change from baseline values during TE period for safety analyses
- In individual subject data listings as appropriate

**Incomplete or missing data** will not be imputed, unless specified otherwise.

**Outliers:** No formal statistical analyses will be performed to detect and/or remedy the presence of statistical outliers, unless specified otherwise.

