Event/ Assessment	Treatment Period					VX-814 Washout Visit 7 (±2) Days After Last Dose of Study Drug	ETT Visit ^c	Safety Follow-up Visit 14 (±2) Days After Last Dose of Study Drug	Safety Follow-up Visit 28 (±2) Days After Last Dose of Study Drug	Comments
	Day 1 ^a	Day 7 (±1) ^b	Day 14 (±2) ^b	Day 21 (±2) ^b	Day 28 (-2) ^c					
Clinic or home health visit		X	X	X	X	X	X	X	X	Subjects will have the option to complete these visits in the clinic or to have a home health visit. Home health visits are only an option if they receive approval from both ethical and regulatory authorities in the respective country.
Telemedicine video conference or telephone contact		X	X	X	X	X	X	X	X	Performed within 1 day after home health visit. Required only for subjects who have a home health visit; not required for subjects who have a clinic visit.
Antigenic AAT level	X	X	X		X	X	X	X	X	Section 11.3
Functional AAT level	X	X	X		X	X	X	X	X	Section 11.3

Table 3-3 Study VX19-814-101 Parts A1, A2, and B: Treatment Period and Follow-up Visits

Event/ Assessment	Treatment Period					VX-814 Washout Visit 7 (±2) Days After Last Dose of Study Drug	ETT Visit ^c	Safety Follow-up Visit 14 (±2) Days After Last Dose of Study Drug	Safety Follow-up Visit 28 (±2) Days After Last Dose of Study Drug	Comments
	Day 1 ^a	Day 7 (±1) ^b	Day 14 (±2) ^b	Day 21 (±2) ^b	Day 28 (-2) ^c					
Weight and height	X									Weight and height will be measured with shoes off.
Standard 12-lead ECG	X	X			X		X	X	X	Performed in triplicate after the subject has rested for at least 5 minutes When ECGs, vital signs, and blood draws are done on the same day, they should be performed in said order. Day 1: predose and 6 hours (±15 min) after dosing. Section 11.5.4
Vital signs	X	X	X		X		X	X	X	Vital signs will be performed after the subject has rested for at least 5 minutes. Section 11.5.3
Pulse oximetry	X	X	X		X		X	X	X	Pulse oximetry will be performed after the subject has rested for at least 5 minutes. Section 11.5.3
Pregnancy test (premenopausal female subjects of childbearing potential only)	Urine and Serum		Serum		Urine		Serum	Serum	Serum	Subjects must have a negative urine pregnancy test result on Day 1 before starting dosing.

Table 3-3 Study VX19-814-101 Parts A1, A2, and B: Treatment Period and Follow-up Visits

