9.1.2 Treatment Period

The Treatment Period will be randomized, double-blind, and placebo-controlled. It will last approximately 28 days. Study drug administration details are provided in Section 9.7.

Subjects who prematurely discontinue study drug treatment will remain in the study from the time of discontinuation of study drug treatment through the last scheduled study visit and complete assessments for all study visits, as described in Section 9.1.4.

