9.1.4 Early Termination of Treatment

If a subject prematurely discontinues study treatment, an Early Termination of Treatment (ETT) Visit should be scheduled as soon as possible after the decision to terminate study treatment. Subjects who prematurely discontinue treatment will be required to complete the Safety Follow-up Visits 14 (± 2) and 28 (± 2) days after their last dose of study drug. The assessments performed at the ETT and Safety Follow-up Visits are listed in Table 3-3.

If the ETT Visit occurs between 12 and 21 days (inclusive) after the last dose of study drug, then the ETT Visit will replace the Safety Follow-up Visit 14 days after the last dose of study drug, and a separate Safety Follow-up Visit 14 days after the last dose will not be required; the Safety Follow-up Visit 28 days after the last dose will be required. If the ETT Visit occurs ≥ 22 days after the last dose of study drug, the ETT Visit will replace the Safety Follow-up Visit 28 days after the last dose, and a separate Safety Follow-up Visit 28 days after the last dose will not be required.

If a subject withdraws consent for the study, no further assessments will be performed. Vertex may retain and continue to use any data and samples collected before such withdrawal of consent.

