9.5 Study Restrictions

Study restrictions and timing of restrictions are summarized in Table 9-1. Subjects may enroll in the study if they are receiving acceptable concomitant medications (according to Table 9-1).

A non-exhaustive list of prohibited medications will be provided in the Study Reference Manual.

Table 9-1 Study Restrictions

Restricted Medication/Food/Activity ^a	Timing of Restriction	
	Start	Stop
Other investigational drugs or devices	28 days before screening, 5 half-lives before screening, or time determined by local requirements (whichever is longer)	Completion of the last Safety Follow-up Visit assessments
Augmentation therapy (human alpha-1 proteinase inhibitor)	More than 42 days before antigenic AAT level is obtained for eligibility	Completion of the last Safety Follow-up Visit assessments
[REDACTED]		
Sensitive CYP2C8 substrates	7 days or 5 half-lives (whichever is longer) before the first dose of study drug	Completion of the last Safety Follow-up Visit assessments
UGT1A1 moderate and strong inhibitors	7 days or 5 half-lives (whichever is longer) before the first dose of study drug	Completion of the last Safety Follow-up Visit assessments
UGT1A1 moderate and strong inducers	14 days before the first dose of study drug	Completion of the last Safety Follow-up Visit assessments
Tobacco products ^c	6 months before screening	Completion of the last Safety Follow-up Visit assessments
Alcohol: no more than 14 drinks/week for females or 21 drinks/week for males (1 drink = 5 ounces (150 mL) of wine or 12 ounces (360 mL) of beer or 1.5 ounces (45 mL) of hard liquor)	Signing of ICF	Completion of the last Safety Follow-up Visit assessments

^a See Section 9.6 for guidance on concomitant medications.

Nicotine replacement therapy under the direction of a physician is allowed.

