9.9 Study Drug Interruption and Stopping Rules

The investigator has the discretion to discontinue study drug treatment at any time if the investigator feels that the subject's continued participation in the study jeopardizes their safety.

Any subject with worsening of AATD or disease progression that, in the judgement of the treating physician, requires (re)initiation of standard of care treatment (per local guidelines) that is prohibited in this study (including augmentation therapy) will discontinue study drug treatment.

Any subject with QTcF values above the threshold values as described in Section 11.5.4 will discontinue study drug treatment.

Study drug treatment may be interrupted for safety concerns at discretion of the investigator.

Study drug administration must be interrupted immediately (before confirmatory testing), and the medical monitor must be notified, if any of the following criteria are met:

- ALT or AST $>5 \times$ ULN
- Total bilirubin $>3 \times$ ULN
- ALT or AST $>3 \times$ ULN associated with total bilirubin $>2 \times$ ULN and/or clinical jaundice

Subjects with new treatment-emergent ALT or AST elevations of $>3 \times$ ULN, or total bilirubin $>2 \times$ ULN, must be followed closely, including confirmatory testing performed within 48 to 72 hours of the initial finding and there must be close monitoring of ALT, AST, and bilirubin levels thereafter, as clinically indicated.

If a subject cannot return to the site for confirmatory testing, a local laboratory may be used. Local laboratory results must be reported immediately to the medical monitor, and the subject must have the tests repeated and sent to the central laboratory as soon as possible (ideally within 48 to 72 hours).

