### **9.3.1 Analysis of Primary Efficacy Variable**

The primary efficacy variable is the change from baseline in plasma functional AAT levels at Day 28.

The observed values and change from baseline of functional AAT levels will be summarized descriptively by treatment group at each visit. The treatment differences of VX-814 400 mg q12h versus placebo and VX-814 600 mg q12h versus placebo in change from baseline of functional

AAT levels at Day 28 will be provided. If the sample size allows, the 2-sided  $P$  values and 95% confidence intervals of the treatment differences will also be provided based on the two-sample  $t$  test.

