### 9.3.2 Analysis of Secondary Efficacy Variable

The secondary efficacy variable is the change from baseline in plasma antigenic AAT levels at Day 28.

The observed values and change from baseline of antigenic AAT levels will be summarized descriptively by treatment group at each visit. The treatment differences of VX-814 400 mg q12h versus placebo and VX-814 600 mg q12h versus placebo in change from baseline of antigenic AAT levels at Day 28 will be provided. If the sample size allows, the 2-sided  $P$  values and 95% confidence intervals of the treatment differences will also be provided based on the two-sample  $t$  test.

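### Should AAT values drawn after a restart of augmentation therapy be kept out of the post-baseline summaries, as they are kept out of baseline?

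*SAP*

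**What the plan says.** SAP 9.1 restricts AAT values by time since augmentation, for baseline only: "only functional and antigenic AAT levels collected >42 days after the last dose of augmentation therapy can be used to define baseline values". Elsewhere in the two documents the 42-day limit serves eligibility.

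Protocol Table 9-1 describes augmentation therapy as human alpha-1 proteinase inhibitor and bars it until the last Safety Follow-up assessments are done. Protocol 9.9 allows for the ban failing: a subject whose worsening "requires (re)initiation of standard of care treatment (per local guidelines) that is prohibited in this study (including augmentation therapy) will discontinue study drug treatment".

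Such a subject does not leave the study. Protocol 9.1.4 arranges an Early Termination of Treatment (ETT) Visit and adds: "Subjects who prematurely discontinue treatment will be required to complete the Safety Follow-up Visits". Protocol 9.1.2 is broader, asking these subjects to "complete assessments for all study visits, as described in Section 9.1.4", yet 9.1.4 names no Day 28 visit. Table 3-3 draws both AAT assays at the ETT Visit and at both Safety Follow-up Visits.

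For the primary variable, SAP 9.3.1 states: "The observed values and change from baseline of functional AAT levels will be summarized descriptively by treatment group at each visit". SAP 9.3.2 says the same for antigenic AAT. Both use the Full Analysis Set, and neither mentions augmentation after baseline.

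**The concern.** Change from baseline has two sides, and the plan protects only one. By refusing AAT drawn within 42 days of augmentation as a baseline, the SAP accepts that such a value reflects infused protein. A post-baseline value drawn soon after a restart has the same defect, but as the visible text stands it would be averaged into its visit row.

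The off-drug rows are where a reader would look to see whether AAT falls back once VX-814 stops. Infused AAT there could pass for a lasting drug effect on an active arm, or for an unexplained rise on placebo. The arms are small, so one subject can move a mean visibly. If such a value also reached the Day 28 comparison, it would touch the primary efficacy result. Dropping it only after seeing unblinded data would be open to criticism.

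**Working it through.** The plan states no figure on this point, so there is none to reproduce. The check asks which samples could be affected, by how much, and whether Day 28 is reached.

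**1. Samples that can follow a restart.** Table 3-3 schedules AAT on Days 1, 7, 14 and 28, at the Washout Visit, at the ETT Visit and at both Safety Follow-up Visits. Because 9.9 ties a restart to stopping study drug, samples taken on treatment come before any restart handled under that rule. That leaves the off-drug visits. Even the ETT sample may come first, since that visit is arranged promptly once the decision to stop is made.

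**2. Position against the 42-day limit.** The later Safety Follow-up Visit falls at most 28 + 2 = 30 days after the last dose. A Safety Follow-up sample taken after a restart that began on or after the last dose is therefore inside 42 days. The ETT Visit has no latest date, so this bound does not cover it.

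Protocol 9.4.1 gives an AAT half-life of about 5 days. The fraction of a rise left after t days is 2^(−t/5):

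- 14 days: 2^(−2.8) = 14.4%
- 28 days: 2^(−5.6) = 2.1%
- 42 days: 2^(−8.4) = 0.3%

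The same formula describes the fall-back of a VX-814 gain, if decay starts at the last dose. An assumed gain of 2 µM leaves 2 × 0.0206 = 0.04 µM at 28 days.

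**3. Shift in a follow-up row.** Planned arm sizes (Protocol 12.1) are 3 at 100 mg, 3 at 200 mg, 6 + 6 = 12 at 400 mg, 15 at 600 mg and 3 + 2 + 5 = 10 on pooled placebo, 43 in all. One subject whose value is raised by D moves the mean by D/n. The documents give no D; 2 to 15 µM is an assumption.

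| Arm | n | Share of D | D = 2 µM | D = 15 µM |
|---|---|---|---|---|
| 600 mg | 15 | 6.7% | 0.13 | 1.00 |
| 400 mg | 12 | 8.3% | 0.17 | 1.25 |
| Placebo | 10 | 10% | 0.20 | 1.50 |
| 100 or 200 mg | 3 | 33% | 0.67 | 5.00 |

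Actual row sizes may be smaller. SAP 9.1 ends the treatment-emergent period at the 14-day visit for subjects consented under CSP Versions 1.0 to 1.2, which suggests that some had no 28-day visit.

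**4. Reach to Day 28.** The 14-day visit falls 12 to 16 days after the last dose. It can land on Days 26 to 28 if the last dose was between Day 10 (10 + 16 = 26) and Day 16 (16 + 12 = 28). Whether it would then count as Day 28 depends on windowing rules that SAP 9.1 cites but that are not in the public text. If it did count, with 10% missing, the shifts for D = 2 to 15 µM would be:

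- 600 mg: n = 13.5, shift 0.15 to 1.11 µM
- 400 mg: n = 10.8, shift 0.19 to 1.39 µM
- placebo: n = 9, shift 0.22 to 1.67 µM

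This needs a restart, a sample after it, a date in that range and a windowing rule that maps it. None of these is established.

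**5. What the analyst already has.**

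- Start and stop dates of all medication (Protocol 9.6).
- Listings of all individual data, and median, minimum and maximum beside each mean (SAP 9.1).
- Important-deviation rules to be finalized before lock (SAP 9.2.6).
- A cleaning review of AAT data, shortly before any planned AAT efficacy analysis, by a biostatistician without treatment codes (Protocol 10.7.1).
- Freedom to amend the SAP before lock (SAP section 4).

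**The case for a change.** The best case for a change is that the plan already states the principle and applies it on one side only. The ban on augmentation governs conduct, not data. The outlier paragraph offers no remedy, and the missing-at-random assumption in Protocol 12.3.3.3 concerns absent values rather than contaminated ones. Keeping every observed value can be defended as a treatment-policy choice, but the visible text does not declare one. A sentence or two would settle it, using dates already collected.

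Much of this stands: the visible text has no such rule, and supplying one would be cheap. Three things weaken the case for requiring it.

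- **Absence is not shown.** The public SAP lacks the windowing rules and contains only Appendices B, C and E. A rule may sit in what is withheld.
- **The event should be uncommon.** Augmentation is barred through follow-up. Exclusion criteria 9 and 22 remove subjects with unstable disease and those for whom stopping augmentation is judged against their interest.
- **Exclusion has its own cost.** The dropped values would come from subjects selected for worsening, which strains the missing-at-random assumption. Keeping and annotating them is a reasonable alternative.

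The worry about post hoc exclusion is also softened, because handling can be fixed before lock and before unblinding.

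**Conclusion.** No change is needed. This is a gap in the visible text that competent analysts would fill sensibly: a team that refuses such values at baseline, holds the medication dates and reviews AAT without treatment codes is well placed to recognize an infused value in a follow-up row and to flag it.

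The established reach is limited to descriptive off-drug rows. Even there it requires a restart before the last follow-up visit, a sample drawn afterwards and no rule in the non-public sections. Per affected subject the shift is D/n, between 6.7% and 33% of D at planned arm sizes. The µM figures rest wholly on an assumed D and are illustrative. No visible objective concerns persistence of effect after dosing, and both efficacy endpoints are at Day 28, so the trial's conclusion does not depend on these rows.

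The judgement assumes that 9.9 is followed, so that on-treatment samples are free of augmentation, and that the windowing rules do not place post-restart samples at Day 28. The difference between Protocol 9.1.2 and 9.1.4 over which visits early stoppers attend is a separate wording matter.

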Event/ Assessment	Treatment Period					VX-814 Washout Visit 7 (±2) Days After Last Dose of Study Drug	ETT Visit ^c	Safety Follow-up Visit 14 (±2) Days After Last Dose of Study Drug	Safety Follow-up Visit 28 (±2) Days After Last Dose of Study Drug	Comments
	Day 1 ^a	Day 7 (±1) ^b	Day 14 (±2) ^b	Day 21 (±2) ^b	Day 28 (-2) ^c					
Physical examination/ review of symptoms	Abbrev PE				Review of symptoms	Review of symptoms	Review of symptoms	Review of symptoms	Review of symptoms	If there are any abnormal findings in the review of symptoms, the subject will be instructed to have a complete PE in the clinic. Section 11.5.3
Spirometry (optional)	X				X					Spirometry will be performed post-bronchodilator and according to the American Thoracic Society Guidelines/European Respiratory Society Guidelines. Section 11.5.5
Sample for UGT1A1 genotype	X									A single sample will be collected at any time on Day 1. Section 11.2.2
Serum chemistry	X	X	X	X	X	X	X	X	X	Section 11.5.2
Hematology	X	X	X	X	X	X	X	X	X	Section 11.5.2
Coagulation	X	X	X	X	X	X	X	X	X	Section 11.5.2
Urinalysis	X	X	X	X	X	X	X	X	X	Section 11.5.2

Table 3-3 Study VX19-814-101 Parts A1, A2, and B: Treatment Period and Follow-up Visits

Event/ Assessment	Treatment Period					VX-814 Washout Visit 7 (±2) Days After Last Dose of Study Drug	ETT Visit ^c	Safety Follow-up Visit 14 (±2) Days After Last Dose of Study Drug	Safety Follow-up Visit 28 (±2) Days After Last Dose of Study Drug	Comments
	Day 1 ^a	Day 7 (±1) ^b	Day 14 (±2) ^b	Day 21 (±2) ^b	Day 28 (-2) ^c					
Blood for PK sampling	X	X	X	X	X	X	X	X	X	Day 1 and Day 28: predose (within 60 minutes before dosing) and at 3 and 6 hours (±30 minutes) after dosing (relative to the morning dose). Days 7, 14, and 21: predose (within 60 minutes before dosing, relative to the morning or evening dose) Safety Follow-up Visits: collected at any time during the visit. Section 11.2.1
Study drug administration	Day 1 through Day 28									Section 9.7
AEs and SAEs	Continuous from signing of ICF through last Safety Follow-up Visit									Section 11.5.1
Medications review	Continuous from signing of ICF through last Safety Follow-up Visit									Section 9.6

AAT: alpha-1 antitrypsin; Abbrev: abbreviated; AE: adverse event; [REDACTED]; ETT: Early Termination of Treatment; ICF: informed consent form; [REDACTED]; PK: pharmacokinetic; SAE: serious adverse event; [REDACTED]

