13.1.1.3 Documentation of Adverse Events

All AEs will be collected from the time the ICF is signed until the following times:

- For subjects who do not enroll: until time of screen failure (e.g., screen failure, withdrawal of consent)
- For enrolled subjects who have a Safety Follow-up Visit 28 days after the last dose: through the Safety Follow-up Visit 28 days after the last dose
- For enrolled subjects who do not have a Safety Follow-up Visit 28 days after the last dose, through the ETT visit if that visit is ≥ 22 days after the last dose of study drug (see Section 9.1.4) or 28 days after the last dose of study drug for subjects who do not have an ETT visit.

All subjects will be queried, using nonleading questions, about the occurrence of AEs at each study visit. When possible, a constellation of signs and/or symptoms will be identified as 1 overall event or diagnosis. All AEs for enrolled subjects will be recorded in the CRF and source document. AEs for subjects who are screened but not subsequently enrolled will be recorded only in the subject's source documents. The following data will be documented for each AE:

- Description of the event
- Classification of "serious" or "nonserious"
- Date of first occurrence and date of resolution (if applicable)
- Severity
- Causal relationship to study drug(s)
- Action taken
- Outcome
- Concomitant medication or other treatment given

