#### **9.4.1 Adverse Events**

AEs will be coded using MedDRA. The number and percentage of subjects experiencing an AE will be summarized by the MedDRA SOC and PT. AEs will be classified as pretreatment or treatment-emergent as follows:

**Pretreatment AEs:** AEs that occurred before the first dose of study drug

**Treatment-emergent AEs:** AEs that worsened or started on or after the first dose date of study drug through the end of the TE Period

**Post-treatment AE:** AE that worsened or that was newly developed after the TE period

For AEs with completely missing or partial start dates, if there is no clear evidence that the AEs started before or after the first dose of study drug, the AEs will be classified as TEAEs.

Imputation rules for missing or partial AE start dates are defined as Appendix C.

AE summary tables will be presented only for TEAEs by treatment group and overall of VX-814 treatment groups, and will include the following:

- Overview of TEAEs
- All TEAEs
- TEAEs by strongest relationship
- TEAEs by maximum severity
- TEAEs leading to death
- Serious TEAEs
- Related TEAEs
- TEAEs leading to treatment discontinuation
- TEAEs leading to treatment interruption

When summarizing the number and percentage of subjects with an event, subjects with multiple occurrences of the same AE or a continuing AE will be counted once. Only the maximum severity level will be presented in the severity summaries, and the strongest relationship level in the relationship summaries.

In addition, a listing containing individual subject level AE data for all deaths, SAEs, treatment discontinuations, and treatment interruptions will be provided separately.

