#### **9.4.2 Clinical Laboratory**

All statistical analyses of laboratory values will be performed using SI units. For treatment-emergent laboratory measurements, the observed values and change from baseline values of the continuous hematology, chemistry, and coagulation results will be summarized by treatment group at each visit.

The number and percentage of subjects with chemistry, hematology and coagulation values meeting threshold analysis criteria during the TE period will be summarized by treatment group. The threshold analysis criterion shift from baseline will also be summarized descriptively. [REDACTED]

In addition, listings containing individual subject hematology, chemistry, and coagulation values outside the reference ranges during the TE Period(s) will be provided. These listings will include data from scheduled and unscheduled visits.

Results of urinalysis and the serum pregnancy test will be listed in individual subject data listings only.

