#### **9.4.3 Electrocardiogram**

For the treatment-emergent ECG measurements, a summary of observed values and change from baseline values will be provided by treatment group at each visit and time point, as applicable, for the following ECG measurements: RR interval (msec), PR interval (msec), QT interval (msec), QTcF interval (msec), QRS duration (msec), and heart rate (beats per minute).

The number and percentage of subjects meeting threshold analysis criteria during the TE Period will be summarized by treatment group. [REDACTED]

Since ECGs are performed in triplicate, the mean of the ECGs will be used as the ECG value for summaries of observed values and change from baseline values, and all reported ECGs will be used to conduct threshold analyses.

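### The TEAE and threshold tables pool subjects counted to about 14 or about 28 days after last dose, depending on consent version, and the visible SAP has no common-window table

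*SAP*

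**What the plan says.** By default, SAP 9.1 ends the TE period at the 28-day Safety Follow-up Visit, at an ETT Visit that replaces it, or at last dose + 28 days. It then sets a second rule: "For subjects consented to the study under CSP Versions 1.0, 1.1, and 1.2, the TE period will include the time period" from first dose to the 14-day visit, a replacing ETT Visit, or last dose + 14 days. Protocol 12.3.1 gives only the 28-day definition.

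The TE period decides what is counted:

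- **Adverse events (SAP 9.4.1).** A post-treatment event is an "AE that worsened or that was newly developed after the TE period", and "AE summary tables will be presented only for TEAEs by treatment group and overall of VX-814 treatment groups". Post-treatment events are therefore outside the summary tables. The measure is the crude number and percentage of subjects.
- **Laboratory (SAP 9.4.2).** "The number and percentage of subjects with chemistry, hematology and coagulation values meeting threshold analysis criteria during the TE period" are summarized by treatment group.
- **ECG (SAP 9.4.3), with the same sentence for vital signs (9.4.4).** "The number and percentage of subjects meeting threshold analysis criteria during the TE Period will be summarized by treatment group".

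SAP 9.1 pools Parts A1, A2 and B unless otherwise specified. The current protocol (13.1.1.3) collects adverse events "through the Safety Follow-up Visit 28 days after the last dose" for enrolled subjects who have that visit. The earlier protocol versions are not provided.

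**The concern.** An event starting 20 days after last dose is a TEAE for a subject on the 28-day rule. For a subject on the 14-day rule it is post-treatment and untabulated, or was never collected. Both subjects sit in the same denominators.

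This would not affect comparisons if every dose group had the same version mix. That is not assured. The 100 and 200 mg groups exist only in Part A1 and the 600 mg group only in Part B (SAP 7.2), so consent version may align with dose. Randomization balances versions in expectation only between arms recruited concurrently within a Part, whereas the tables pool Parts.

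Safety is a primary objective, and Protocol 5.2 gives identifying an optimal dose as part of the study's purpose. If the mix differs, percentages side by side in one table are counted over different follow-up, and the table does not show it.

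**Working it through.** **1. Window lengths.** The Protocol Synopsis gives 28 days of treatment plus 28 of follow-up: 28 + 28 = 56 days, which matches its stated duration. The early-version rule gives 28 + 14 = 42 days. The ratio is 56/42 = 1.33. These are nominal, because the visits have a ±2-day window.

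**2. Group sizes (SAP 7.2).** Part A1: 6 + 3 + 3 + 3 = 15. Part A2: 6 + 2 = 8. Part B: 15 + 5 = 20. The total is 43, as stated. Pooled: 100 mg 3, 200 mg 3, 400 mg 12, 600 mg 15, placebo 3 + 2 + 5 = 10.

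**3. When the distortion is zero.** This holds if every group has the same version mix, or if no subject has a first event 15 to 28 days after last dose.

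**4. TEAE illustration.** Assumptions, none from the documents: true incidence over 56 days is 30% in every group; the event rate is constant over the first 42 days and r times that rate in days 15 to 28 after last dose. With H = −ln(1 − 0.30), the 42-day incidence is 1 − exp(−H × 42/(42 + 14r)).

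| r | 42-day incidence | Gap from 30% |
|---|---|---|
| 0 | 30.00% | 0 |
| 0.25 | 28.05% | 1.95 points |
| 0.5 | 26.34% | 3.66 points |
| 1 | 23.47% | 6.53 points |

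The gap column applies only if one group is wholly on the short window and the other wholly on the long one. At r = 1 it is 2.40 points for a 10% incidence and 9.46 for 50%.

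**5. Version following Part exactly (assumption: A1 and A2 on 14 days, B on 28 days).**

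- r = 1: placebo = (5 × 23.47 + 5 × 30)/10 = 26.74%. The 400 mg group reads 23.47%, 3.26 points lower (12 × 0.0326 = 0.39 subject). The 600 mg group reads 30.00%, 3.26 points higher (15 × 0.0326 = 0.49 subject). Overall VX-814 = (18 × 23.47 + 15 × 30)/33 = 26.44%, 0.30 points below placebo.
- r = 0.25: placebo = 29.03%; the differences are −0.97 and +0.97 points (0.12 and 0.15 subject).

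**6. Only Part A1 on the short window (assumption), 20% incidence, r = 1.** Crude rates would be 15.4% (100 and 200 mg), 17.7% (400 mg), 18.6% (placebo) and 20.0% (600 mg).

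**7. Threshold tables.** Assume the earlier schedule equals current Table 3-3 without the column "Safety Follow-up Visit 28 (±2) Days After Last Dose of Study Drug". Scheduled post-baseline time points for completers are then:

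- Laboratory: Days 7, 14, 21, 28, washout and 14-day visit = 6; with the 28-day visit, 7.
- ECG: the 6-hour reading on Day 1 ("Day 1: predose and 6 hours (±15 min) after dosing"), Days 7 and 28, and 14-day visit = 4; with the 28-day visit, 5.
- Vital signs: Days 7, 14, 28 and 14-day visit = 4; with the 28-day visit, 5.

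With an equal, independent chance per time point and 30% over the longer schedule, the shorter schedule gives 1 − 0.7^(6/7) = 26.34% for laboratory (gap 3.66 points) and 1 − 0.7^(4/5) = 24.82% for ECG and vital signs (gap 5.18 points). If version followed Part, the differences from pooled placebo would be half of these: 1.83 and 2.59 points.

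**The case against.** The strongest reply is that no harm can be shown. Neither document gives the consent-version mix. Parts A2 and B may open before Part A1 is full, so the mix may be similar across groups. Even with version following Part and an undiminished off-drug rate, the illustrated shift is under half a subject per group. All of this stands.

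A reader might infer that the 14-day rule is an error, or that it contradicts Protocol 12.3.1. The documents do not support that. The rule is prespecified and tied to earlier protocol versions, and it probably mirrors the follow-up those subjects had. A reader might also infer that the dose comparison is biased in a known direction. That too is unsupported without the version mix.

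Much of the safety reporting is largely untouched. An event starting 15 to 28 days after last dose cannot have led to discontinuation or interruption, so those tables hardly change. By-visit summaries and individual listings are also largely unaffected, and no safety hypothesis is tested. The threshold figures rest on an earlier schedule that cannot be seen. Text after the threshold sentences in SAP 9.4.2 to 9.4.4 is blacked out and the visit windowing rules are not visible, so absence of a remedy is shown only for the visible text.

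The reply does not remove the gap in the main TEAE tables. SAP 9.4.1 shows no blacked-out text and offers no common-window table. Listings let a reader rebuild event timing by hand, but they do not replace a comparable table.

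**Conclusion.** The point holds as a minor comparability gap in descriptive safety reporting. The plan can place percentages counted over about 42 and 56 days side by side without showing it.

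The size is unknown and may be zero. In the illustration (30% over 56 days, version following Part), 400 mg and 600 mg read about 3.3 points below and above pooled placebo if the off-drug rate is undiminished, and about 1 point if it falls to a quarter. The 6.5-point gap needs complete separation of windows between two groups as well as an undiminished rate, and it bounds the effect at that incidence only if the late rate does not exceed the earlier one. Efficacy, sample size and error rates are unaffected.

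**What to change.** Keep both TE definitions for all-event reporting. Amend SAP 9.1 and 9.4 before database lock, as SAP section 4 allows:

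1. For between-group comparison, add TEAE tables by treatment group cut at a fixed last dose date + 14 days for every subject, whenever the 14-day or ETT Visit occurred. Note that a subject seen on day 12 or 13 may have up to 2 days less follow-up.
2. Add threshold tables restricted to measurements through the 14-day visit window: 14 + 2 = 16 days after last dose.
3. List later events separately, with the number of subjects actually followed beyond that point.
4. Report the number consented under Versions 1.0 to 1.2 by treatment group and Part.
5. Footnote any table that mixes the two windows.

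The cut should be a calendar date, not a visit. The 14-day visit has a ±2-day window, and under Protocol 9.1.4 an ETT Visit 12 to 21 days after last dose can replace it, so a visit-based end would leave a spread of up to 21 − 12 = 9 days.

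The cost is one derived date, an extra set of tables, and a shorter window in the comparison tables only. No new data are needed.
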